In the last 10 years, there has been an increased interest in using tDCS to modulate cognitive functions in healthy individuals as well as in individuals with various disorders. In addition to its appeal as an effective adjunctive intervention, there are several reasons for this increased interest in tDCS research. One reason pertains to safety considerations: tDCS seems to have no significant adverse side effects, provided that stimulation parameters are kept within safety limits (see Nitsche et al., 2008; Poreisz et al., 2007). In a meta-analysis study, the most common adverse sensation was mild tingling and mild itching under the electrodes and seldom-occurring headache, fatigue, and nausea (Poreisz et al., 2007). Furthermore, tDCS is not reported to provoke seizures and current tDCS protocols are not found to induce brain edema or changes in the blood brain barrier (Nitsche et al., 2004). A second benefit of tDCS pertains to portability and cost. The tDCS apparatus is more portable, less expensive, and easier to use than other technologies, like transcranial magnetic stimulation (TMS). These features allow treatment to be delivered not only in clinical settings, but also in a patient's own home. Third, tDCS allows one to easily conduct placebo (sham) stimulation-controlled studies, because, with the exception of a slight itching and mild tingling sensation, participants rarely experience sensations related to the stimulation. A method to blind participants as to whether they are receiving real or sham tDCS in a research treatment protocol is turn the tDCS stimulator on for 30 seconds at the start of the sham condition to induce scalp sensations associated with stimulation, and then gradually decrease and turn off tDCS within the next 15 seconds (Gandiga et al., 2006). Finally, tDCS is also well suited to neuromodulation concurrent with behavioral SALT. For example, Broca's area (inferior frontal cortex) can be easily and comfortably targeted with tDCS along with behavioral treatment for naming.

Mechanism of tDCS

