After informed consent is received, a neurological examination will be performed and multiple screening assessments will be conducted including a tDCS and MRI safety screening (see below). If the participant passes the initial screening portion, speech and language diagnostic testing will be conducted during the same visit (Visit 1). During the next visit (Visit 2), participants will undergo a second baseline assessment of naming ability and assessment of connected speech. On that visit, participants who have no contraindication for MRI will be randomized to (1) fMRI electrode placement or (2) structural electrode placement. All participants who have no contraindication will have structural and rsfcMRI. Those randomized to fMRI electrode placement will also participate in the naming paradigm during the MRI. Participants may also undergo fNIRS at this visit. The third visit will include electrode positioning and tDCS treatment administration. Participants will receive 15 sessions (Visits 3-17) of tDCS + SALT administration. At the beginning of Visit 3, eligible participants will be randomized to receive either A-tDCS (1 mA) or sham-tDCS (placebo) for 15 sessions (20-minutes per each 45-minute behavioral treatment session) over the course of three weeks. A computer-delivered naming treatment will be coupled with the stimulation. The computer-delivered treatment task will be 45-minutes in total length, so that it will commence at the same time as the tDCS administration and continue for another 25-minutes after the tDCS has ceased. To assess cardiovascular arousal, blood pressure and heart rate will be measured before and after each session. Additionally, discomfort ratings will be recorded following the end of each session using the Wong-Baker FACES Pain Rating Scale (Wong & Baker, 1988) and a weekly neurological exam will be administered by a neurologist.

Neither the participant nor the clinician monitoring and setting up the treatment will have knowledge of the treatment condition (A-tDCS versus sham).

Date: March 2, 2021

Principal Investigator: [name], MA

Application Number: IRB00089018

Utilizing a computerized picture naming assessment (PNT), all participants will be assessed at several different time points throughout the experiment: twice immediately before and twice the week immediately following the fifteenth and final treatment session; twice at five weeks follow-up after the end of treatment; and twice at 20 weeks after the end of treatment.

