9. Instruct the participant how to perform the self-administered computer-delivered naming treatment, consisting of a picture/seen and heard spoken word verification task, which will be coupled with the stimulation. The computerized treatment task will be 45-minutes in total length, so that it will commence at the same time as the tDCS administration. A picture will be presented for 2 s on a laptop computer screen and will be immediately followed by an audio-visual display of a male speaker's mouth saying a noun. Video of the speaker producing the noun is presented in synchrony with the audio via in-ear headphones. The spoken word either will or will not match the preceding picture. In the event of a match, instruct the participant to press a large green response button interfaced with the computer, and in the case of a non-match, instruct the participant to press a red button. Half of the picture/word pairs will match, while the other half will not. The computer will provide immediate visual feedback following a response in the form of a "smiley face" for correct answers and a "frowny face" for incorrect answers. Additionally, following the completion of a treatment session, a data file of the participant's responses will be automatically saved, and the accuracy score from that session will be displayed on the computer screen.
10. "Click" on the START icon on the "blinding" computer to simultaneously start stimulation and the computer treatment task.
11. Measure and record the participant's blood pressure and heart rate following treatment completion.

Date: March 2, 2021

Principal Investigator: [name], MA

Application Number: IRB00089018

12. Record any Adverse Events experienced during the treatment session or since the last visit on the AE log.

13. Assess and record the participant's comfort rating using the Wong-Baker FACES Pain Rating Scale following treatment completion.

Procedures for Neurological Examination (Visits 8, 13, 18)

The following procedures will be performed:

1. All participants will be monitored closely for safety and neurological functioning during the duration of the study. In addition to the comfort ratings recorded daily the neurological examination administered during Visit 1 will be re-administered weekly by [name] during the treatment phase.

b. Study duration and number of study visits required of research participants.

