12. SAFETY ANALYSES

All adverse events will be summarized in terms of frequency, severity and relatedness to the study intervention using the MedDRA code. All subjects who received at least one session of A-tDCS or S-tDCS will be included in the safety analysis. The cumulative incidences of adverse events will be compared between the treatment groups using Fisher's exact test at the two-sided alpha level of 0.05.

References

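### The only planned between-arm comparison of adverse events counts each participant once across 15 sessions, so it can miss a difference in how often a common, recurring event happens

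*SAP*

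**What the plan says.** Protocol section 4a sets the schedule: "Participants will receive 15 sessions (Visits 3-17) of tDCS + SALT administration". Step 12 of its treatment procedures tells staff, at every session, to "Record any Adverse Events experienced during the treatment session or since the last visit on the AE log".

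SAP section 12 gives the analysis. First comes a description: "All adverse events will be summarized in terms of frequency, severity and relatedness to the study intervention using the MedDRA code". Then comes the comparison: "The cumulative incidences of adverse events will be compared between the treatment groups using" "Fisher's exact test at the two-sided alpha level of 0.05". The safety analyses in protocol section 7c name the same test. SAP section 5.4 admits to the safety sample anyone who received at least one session.

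On expected harms, the protocol background reports from earlier work that "the most common adverse sensation was mild tingling and mild itching under the electrodes", with headache, fatigue and nausea seldom. It also describes a sham method: "turn the tDCS stimulator on for 30 seconds at the start of the sham condition to induce scalp sensations".

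On session-level tolerability, protocol section 4a says "discomfort ratings will be recorded following the end of each session using the Wong-Baker FACES Pain Rating Scale", and section 7c plans a repeated-measures proportional odds model for these ratings. SAP section 12 does not contain that model. SAP section 2 says that the final SAP takes precedence over the protocol and will be updated before database lock.

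**The concern.** Fisher's exact test on a cumulative incidence works from a 2x2 table of participants with and without the event. Repeat events in one person disappear, and a person who attended one session weighs the same as one who attended 15. For an event that happens once and is rare, this is the natural summary. For one that can return at every stimulation, the share of people ever affected rises towards 100% in both arms as sessions accumulate. A real difference in how often people are affected then shrinks to a small difference in how many were ever affected.

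At stake is the tolerability statement, not the efficacy result. A non-significant comparison of cumulative incidence could be read as equal tolerability when it carries little information on that question.

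**Working it through.** **The plan's own figure.** The only power figure in the documents is for efficacy: 89% with 20 per arm, difference 23, SD 22.2, two-sided alpha 0.05 (SAP section 8.3). The standardised difference is 23/22.2 = 1.036, the noncentrality is 1.036 × √(20/2) = 3.28 on 38 degrees of freedom, and the power is 0.891. It reproduces. No power is stated for safety.

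**Inputs.** 15 sessions (protocol section 4a); 1:1 allocation and a target of 50, so 25 per arm (SAP section 4); Fisher's test at two-sided 0.05 (SAP section 12). Per-session event rates and within-person clustering are assumptions, because the documents give neither. All calculations take 15 sessions as attended.

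**Ever-affected proportion.** With independent sessions it is 1 − (1 − p)^15. For p = 0.20 this is 1 − 0.80^15 = 96.5%; for p = 0.40 it is 1 − 0.60^15 = more than 99.9%. A twofold difference in frequency becomes a ratio of 1.04. With clustering, a beta-binomial model with intraclass correlation ICC gives 1 − ∏(b + i)/(a + b + i) for i = 0 to 14, where a = p(1 − ICC)/ICC and b = (1 − p)(1 − ICC)/ICC.

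**Power to detect a doubling, 25 per arm.** Fisher power is by full enumeration. The session-level column is a Welch t-test on each person's proportion of sessions affected (4,000 simulations; simulated size 0.049-0.051).

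| ICC | Per-session rate, sham vs active | Ever affected | Fisher | Session-level |
|---|---|---|---|---|
| 0 | 5% vs 10% | 54% vs 79% | 38% | 74% |
| 0 | 10% vs 20% | 79% vs 96% | 27% | 96% |
| 0 | 15% vs 30% | 91% vs 99.5% | 2% | >99% |
| 0 | 20% vs 40% | 96.5% vs >99.9% | <0.1% | about 100% |
| 0.1 | 20% vs 40% | 86% vs 99% | 10% | 97% |
| 0.3 | 2% vs 4% | 10% vs 19% | 7% | 7% |
| 0.3 | 10% vs 20% | 41% vs 66% | 37% | 40% |
| 0.3 | 20% vs 40% | 66% vs 90% | 42% | 74% |
| 0.3 | 40% vs 80% | 90% vs 99.6% | 3% | >99% |
| 0.5 | 10% vs 20% | 29% vs 50% | 27% | 26% |
| 0.5 | 20% vs 40% | 50% vs 77% | 42% | 55% |

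Over all settings tried (sham rate 2-40%, ICC 0-0.5, 20 or 25 per arm), Fisher power for a doubling never exceeded 47%.

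**A second model.** Let each person's log-odds vary normally with SD 0.5, 1 or 1.5, and compare session counts with a rank test. At 20% vs 40%, ever-incidence is about 93% vs 100%, 84% vs 97% and 75% vs 92%. Fisher power is about 1%, 11% and 25%; the rank test has about 99%, 90% and 75%. At 2% vs 4%, ever-incidence is only 19-25% vs 32-44%, and at 5% vs 10% it is 36-51% vs 54-75%. Neither is near saturation. At 5% vs 10%, power is about 20-32% for Fisher and 31-59% for the rank test.

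**Rare events.** For 5 of 25 against 0 of 25, the two-sided Fisher p is 2 × C(25,5)/C(50,5) = 2 × 53,130/2,118,760 = 0.0502. For 6 of 25 against 0 it is 0.022. This is a small-sample limit and has nothing to do with saturation, but it shows why an interval says more than the p-value alone.

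**The case against.** Several parts of the case against stand.

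- **The rates are assumed.** With independent sessions, saturation needs a sham rate of roughly 10-15% per session or more, and with ICC 0.3 about 30-40%. Below that, Fisher's test is weak because the trial is small, and session-level data help less or not at all.
- **Tingling and itching may never reach the adverse event log.** The documents do not say that they do. Protocol section 8c has the study physician and DSMB notified at once of any adverse event. At 20% and 40% of sessions that would mean 375 × 0.20 + 375 × 0.40 = 225 notifications, which makes routine logging doubtful. Against this, the same section wants all adverse events recorded whatever their intensity. The question stays open.
- **The sham description is background.** It reports a blinding method from the literature, not this trial's stated sham settings, so it shows only that sham may also produce sensations.
- **The protocol does plan a session-level safety model.** The FACES model uses ratings from every session. It addresses pain ratings rather than adverse events, though, and the SAP omits it.
- **A frequency summary is planned.** It might expose a difference, but SAP section 12 does not say whether it counts events or people, and gives no denominator or interval.

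A reader might infer that the plan will overstate tolerability and so distort the decision on a Phase III trial. The documents do not support that: protocol section 7c ties that decision to the primary efficacy test and treats safety analyses as exploratory.

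**Conclusion.** The point holds conditionally. Fisher's test on cumulative incidence is the only planned between-arm comparison of adverse events. It discards recurrence and sessions attended, although events are recorded at every session. If recurring sensations are logged as adverse events and are moderately common, a doubled per-session frequency can pass as similar incidence. At 20% vs 40% with 25 per arm, power is about 1-25% against 75-99% under the normal log-odds model. Under the beta-binomial model it runs from under 0.1% against about 100% (independent sessions) to 42% against 55% (ICC 0.5). At sham rates of 2-5% there is no saturation, and with strong clustering the advantage of session-level data can disappear. It does not follow that harm will be hidden, only that the stated comparison could not be relied on to show it. The primary result is unaffected. This is an inexpensive improvement to the safety section.

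**What to change.** In SAP section 12:

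1. Keep the cumulative-incidence table and add the risk difference with an exact 95% CI.
2. For events logged at treatment sessions, add by arm the proportion of attended sessions affected. Compare arms with a subject-clustered model (GEE logistic with a small-sample variance correction, or an overdispersed binomial), using sessions attended as the denominator, and label it exploratory.
3. State which logged terms this table covers, and how events noted as occurring since the last visit are assigned.
4. Carry the protocol's repeated-measures proportional odds model for the FACES ratings into the SAP, so that it is not lost when the SAP takes precedence.

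The cost is SAP wording, one more table and a little more analysis. The SAP is due for an update before database lock in any case. The new table uses data already collected, provided that the log dates each occurrence; the documents do not show its layout. No trial procedure changes.
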